9.2 Description of trial subject groups

For Part B, all statistical analyses described below will be performed.

Subjects have been randomised to one of the two intervention groups

- BNT162b2 (Comirnaty) and
- mRNA-1273 (Spikevax).

Patient Cohorts, arm and study **Intervention group in Part B:**

Cohort	Vaccination prior to study entry	Arm	Study intervention: 4 th vaccination dose*
Cohort 4	BNT162b2 +	7	BNT162b2
	BNT162b2 + BNT162b2	8	mRNA-1273
Cohort 5	BNT162b2 +	9	BNT162b2
	BNT162b2 + mRNA-1273	10	mRNA-1273

Cohort 6	mRNA-1273 + mRNA-1273 + mRNA-1273	11	BNT162b2
		12	mRNA-1273
Cohort 7	mRNA-1273 + mRNA-1273 + BNT162b2	13	BNT162b2
		14	mRNA-1273
Cohort 8	ChAdOx-1-S + ChAdOx-1-S + BNT162b2	15	BNT162b2
		16	mRNA-1273
Cohort 9	ChAdOx-1-S + ChAdOx-1-S + mRNA-1273	17	BNT162b2
		18	mRNA-1273

Each of the initial prime boost strategies (see first column in table above) define a cohort of patients. If not otherwise stated, all descriptive analyses described below will be performed overall and separately for cohorts.

Patient demographics and baseline characteristics will be summarised on the modified ITT (mITT) set, overall and by treatment cohort and randomised treatment arms, by means of summary descriptive statistics. Summaries of baseline clinical laboratory values will be presented by overall, treatment arm and by treatment cohort and randomised treatment arms.

For qualitative variables (e.g., gender (biological sex)), absolute and relative frequencies will be calculated per treatment group. Data will be visualised by bar plots. For quantitative data (e.g., age), the number of valid observations, mean, standard deviation, standard error, median, minimum and maximum will be calculated for each treatment group and each time point separately. Data will be visualised by waterfall, boxplots and histograms.

9.3 Primary Endpoint Analysis

All primary analyses will be on the mITT set, consisting of all randomised subjects whose primary endpoint measurement is available. The primary endpoint is the rate π of 2-fold antibody titre increase following the 4th vaccine dose measured by quantitative enzyme-linked immunosorbent assay (Anti-RBD-ELISA) against wildtype virus at 14 days after the 4th vaccine dose (versus immediately before vaccination).

For the binary primary endpoint absolute and frequencies in percent will be calculated for each intervention group in Part B. For each treatment group in part B the corresponding rate together with simultaneous 95% confidence intervals will be calculated. Exact Clopper Pearson confidence

intervals at Bonferroni adjusted level of $(1-0.05/2) * 100\%$ will be provided (as there are two treatment groups in part B).

9.3.1 Supportive analyses for the primary endpoint

In additional supportive analysis, the primary endpoint will be determined in the same way for each cohort separately, i.e., further supportive analyses will be performed based on different pre-vaccination series. Especially, within each cohort the multiplicity adjustment will be implemented as described above. The data will be visualised with bar charts.

To evaluate whether there is a difference between the two randomised intervention groups in the binary primary endpoint, a Cochrane-Mantel-Haenszel test will be applied stratified by the initial cohort vaccine strategy (cohort 4 to 9).

Furthermore, a logistic regression model will be performed using the primary endpoint as dependent variable. In the logistic regression models intervention group will be used as main factor. Based on the logistic regression model odds ratio (OR) and the corresponding 95% confidence intervals will be reported to evaluate whether there are differences between the two study intervention groups. In the logistics analyses we will also adjust for factors such as initial vaccination regimens (factor cohort), age and sex. We will also account for the different time lags between the 2nd and 3rd doses in further sensitivity analysis, e.g., including the number of days between vaccinations as additional covariate in the analysis models. Furthermore, descriptive tables will be provided stratified by taking into consideration the vaccination regimens.

In addition to the binary primary endpoint, the antibody titre values of visit 1 and 2 will be analysed on the metric scale (see analyses planned for secondary endpoints).

9.3.2 Impact of Covid infections between baseline and day 14

With testing for anti-Nucleocapside IgG at visits 1 (baseline), visit 2 (=d14) and visit 5 (end of study) subjects will be assessed for SARS-CoV-2 infection since randomization. Overall and for all vaccination regimens the proportion of infections between d0 and d14 (based on an anti-Nucleocapside IgG at visit 2 indicative of SARS-CoV-2 infection) will be compared descriptively.

In further logistic regression models the impact of having had a Covid infection between visit 1 and visit 2 on the primary endpoint will be explored by using it as additional factor.

Additionally, a sensitivity analysis will be performed on the per protocol analysis set, including only subjects who have been vaccinated and not having had a new infection between visit 1 and visit 2 using the anti-Nucleocapside IgG measurements of visit 1 and 2.

For subjects where the exact timepoint of an externally confirmed infection is available (i.e. subjects reports date of a SARS-CoV-infection confirmed outside study procedures, captured by AE reporting), a further sensitivity analysis will be performed excluding only those patients who had a an externally confirmed infection between randomisation and the observation of the primary endpoint.

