9.4.3 Linear Models & Adjustment for Covariates and Mixed Models

When analysing the data from all study visits (e.g., Visit 1, Visit 2 and Visit 5 for immunogenicity data such as Anti-RBD or anti-N IgG), mixed model for repeated measurements (MMRMs) will be applied using subject ID as random factor using an unstructured covariance matrix. The last value before randomisation (baseline) will be used as covariate in the MMRM.

Similarly as described for the logistic regression models for the primary endpoint (see supportive analyses for the primary endpoint), also in the MMRs we adjust for factors/covariates such as initial vaccination regimens (factor cohort), age and sex. We will also address for the different time lags to previous vaccinations, e.g., for the time between the 2nd and 3rd doses and between the 3rd and 4th doses, respectively in further sensitivity analysis, e.g., including the number of days between vaccinations as additional covariate in the analysis models.

The impact of new covid infections after baseline on the secondary endpoints will be explored similarly to the primary endpoint analysis. For example by using an additional factor (New Covid Infections based on anti-Nucleocapside IgG between visits) in the MMRMs and performing analysis on the PP analysis set.

In further secondary analyses, it will be explored whether switching or keeping the same vaccine product for the 4th vaccination (study intervention in B) compared to the 3rd vaccination will have an effect. To evaluate such an impact models will be performed using for example the interaction between cohort and study drug or an indicator variable whether the 4th and 3rd vaccination are the same or not.

In addition to using the log10 scaled GMT values (=y) as dependent variable, we will use the relative change compared to the baseline value as dependent variable. The relative change is defined as $(Y_{\text{visit}} - Y_{\text{baseline}}) / Y_{\text{baseline}}$. The change might be presented as percentage change.

The secondary analyses will be performed overall and for cohorts separately.

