9.8 Multiplicity adjustment

The different pre-study vaccine combinations are considered as inferentially independent, as the prior vaccination strategy cannot be influenced and there will be no extrapolation from one cohort to another one for the primary analysis. Therefore, the multiplicity adjustment concerning the primary endpoint will be applied within each cohort, but there will be no further adjustment for having several cohorts within the accompanying master protocol. The comparison of treatment group is of secondary purposes, which are not subject of further multiplicity adjustments.

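### SAP 9.3.1 does not name the visit-1 anti-RBD titre as a covariate in the supportive logistic responder model; pre-specifying it would usually sharpen the arm comparison, by an amount the documents do not fix

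*SAP*

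**What the plan says.** - **Endpoint.** SAP 9.3 defines the primary endpoint as the rate of 2-fold anti-RBD titre rise "at 14 days after the 4th vaccine dose (versus immediately before vaccination"). The visit-1 titre is therefore the denominator.
- **Primary analysis.** SAP 9.3 plans one Clopper-Pearson interval per randomised group. It contains no contrast between the groups.
- **Arm comparison on this endpoint.** SAP 9.3.1, on supportive analyses, first plans a CMH test stratified by cohort, then a logistic model from which "odds ratio (OR) and the corresponding 95% confidence intervals will be reported". On covariates it says: "In the logistics analyses we will also adjust for factors such as initial vaccination regimens (factor cohort), age and sex".
- **Further logistic models.** A sensitivity analysis in 9.3.1 accounts for the gap between doses 2 and 3, "including the number of days between vaccinations as additional covariate in the analysis models". In SAP 9.3.2, "the impact of having had a Covid infection between visit 1 and visit 2 on the primary endpoint will be explored" by adding an infection factor. None of these models names the visit-1 titre.
- **Repeated-measures model.** SAP 9.4.3 does use it: "The last value before randomisation (baseline) will be used as covariate in the MMRM".
- **Status.** SAP 9.8 states: "The comparison of treatment group is of secondary purposes, which are not subject of further multiplicity adjustments".

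**The concern.** A participant who enters with a high titre usually finds it harder to double it, so the visit-1 value is likely to be a strong predictor of response. It is measured before the dose at visit 1, and nobody can have a valid endpoint without it, so including it loses no participants. The same SAP accepts it as a covariate for the continuous titre and gives no reason for treating the binary model differently.

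The stated primary objective is to compare immune response between arms, while the primary analysis only estimates each group's rate. Readers wanting a contrast on the responder endpoint will turn to 9.3.1. At stake is the precision of that contrast. There is also a pre-specification issue: the trial is unblinded and the SAP plans no blind data review, so an open covariate list leaves an influential modelling choice until after the data are seen.

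**Working it through.** **1. The plan's own figure.** Inputs from SAP 12.1: 250 per group, rate 0.50, Bonferroni for two intervals (z = 2.2414).

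Half-width = 2.2414 × √(0.25/250) = 0.0709, which reproduces the stated ±7.1 points. For dropout, 500/0.92 = 544 and 500/0.90 = 556, so 550 lies between. These figures concern interval width. No power is stated for the logistic comparison.

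**2. When the visit-1 titre predicts response.** Let B and P be log10 titres at visits 1 and 2, with SDs sB and sP and correlation ρ. Response means P − B ≥ log10(2). The correlation of the rise with baseline is

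(ρ·sP − sB) / √(sB² + sP² − 2ρ·sB·sP).

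With sB = sP = 0.4 and ρ = 0.5 this is (0.20 − 0.40)/0.40 = −0.50, so baseline explains 25% of the variance of the rise. With sB = 0.3, sP = 0.4 and ρ = 0.7 it is −0.02/0.286 = −0.07, almost nothing. Being the denominator makes baseline a likely predictor, not a certain one.

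**3. Power with and without it.** None of the SDs, correlations, rates or differences below is in the documents; all are assumed.

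Simulation: 250 per arm, 1,500 runs per cell, two-sided Wald test at 0.05. A logistic model on arm, cohort, age and sex was compared with the same model plus log10 visit-1 titre. Responder rates were about 0.50 v 0.61, 0.65 v 0.75 and 0.80 v 0.89. The table gives the gain in power, in percentage points, over these three rate pairs.

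| SD visit 1 / visit 2 | ρ = 0.3 | ρ = 0.5 | ρ = 0.7 | ρ = 0.85 |
|---|---|---|---|---|
| 0.40 / 0.40 | 7.0 to 11.5 | 3.8 to 7.1 | 2.0 to 4.0 | 2.0 to 3.1 |
| 0.45 / 0.30 | 14.5 to 22.1 | 15.3 to 17.1 | 12.1 to 19.4 | 13.6 to 19.9 |
| 0.30 / 0.40 | 2.5 to 6.5 | 2.1 to 2.6 | −0.1 to 0.3 | −0.1 to 0.9 |

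Power without the titre was 0.66 to 0.81. As a check, the usual two-proportion formula for 0.50 v 0.61 gives pooled SE √(2 × 0.555 × 0.445/250) = 0.0445 and unpooled SE √((0.25 + 0.2379)/250) = 0.0442. Then (0.11 − 1.96 × 0.0445)/0.0442 = 0.52, a power of about 0.70, in line with the simulated 0.66 to 0.72 for that rate pair.

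The Monte Carlo SE of a power near 0.70 is √(0.7 × 0.3/1500) = 1.2 points, so differences of a point or two between cells mean little. With a larger effect (geometric mean ratio 1.5), power without the titre is already 0.87 or more and the gain falls to between 0 and 7 points.

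**4. Type I error.** Over 3,000 null runs, the rejection rates without and with the titre were 0.047 and 0.045 (ρ = 0.3), and 0.055 and 0.058 (ρ = 0.7). Neither model is in trouble.

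**5. Chance imbalance.** Assume SD 0.4, ρ = 0.5 and rates near 50%. The SE of the baseline difference between arms is 0.4 × √(2/250) = 0.036 log10. A one-SE imbalance shifts the mean rise by 0.5 × 0.036 = 0.018 and the responder difference by 0.018 × 0.399/0.4, about 1.8 points. The SE of the unadjusted difference is √(2 × 0.25/250) = 4.5 points, which already contains that component.

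**6. Effect on the odds ratio.** At 0.50 v 0.61 with SDs of 0.40 and ρ = 0.5, the average odds ratio moves from 1.58 to 1.74. This is a change of estimand from a less to a more conditional odds ratio, not a larger vaccine effect.

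**The case against.** The other side has good points, and most of them stand.

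- **The list is open.** A reader might infer that the SAP decided against the visit-1 titre. It did not; the covariates are introduced as examples. The defect is that the most relevant one is not pre-specified.
- **The analysis is subordinate.** It is supportive, SAP 9.8 makes group comparison secondary, and no power target was set. The primary intervals do not depend on it.
- **It is not the only adjusted comparison.** The CMH test already stratifies by cohort.
- **Baseline adjustment is planned elsewhere.** SAP 9.3.1 sends the titres to metric-scale analyses, and the 9.4.3 model adjusts the continuous titre for baseline without losing information to a cut-off. That softens the point but gives no adjusted contrast on the responder endpoint itself.
- **Chance imbalance is not bias.** A reader might infer that the planned odds ratio is biased because randomisation is not stratified by titre. Steps 4 and 5 show otherwise: the interval covers such imbalance on average, and the error rate is about 5% either way.

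One possible substitute fails. Prior COVID-19 infection, a randomisation stratum that 9.3.1 also leaves unnamed, changed power by at most about 2 points when added alone (assuming 20% previously infected with baseline 0.25 log10 higher), so it does not stand in for the titre.

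**Conclusion.** The point holds as one of pre-specification and precision in a supportive model. The visit-1 titre should be named in the logistic responder model: it is part of the outcome's definition, always available when the endpoint is, and already used in the SAP's repeated-measures model.

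The gain cannot be given as a single figure. At 250 per arm and power of roughly 0.66 to 0.81 without the titre, it is about 2 to 12 points if the SDs are equal at both visits. It is about 0 if baseline is less variable than day 14 and highly correlated with it, and up to about 22 if baseline is more variable. A reader might infer a definite loss that applies in most settings; the documents supply none of the quantities needed to say so. Nor do they support any inference that the primary result is affected.

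**What to change.** In SAP 9.3.1, name log10 visit-1 anti-RBD titre as a continuous covariate in the main logistic model, beside cohort, age and sex. Define it as the same pre-dose value that forms the endpoint's denominator, with values outside the assay range handled under SAP 9.6. Report the model-standardised risk difference with 95% CI beside the odds ratio, and label the odds ratio as conditional. Leave the Clopper-Pearson intervals and the CMH test unchanged.

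The cost is a sentence or two in the SAP and one extra standardisation step in the analysis; no new data are needed. The small downside is that the conditional odds ratio lies further from 1 than the one without the titre. The standardised risk difference deals with this, because it can be read directly against the two primary rates.

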4.7. Treatment

4.7.1. Treatments to be given

According to section 4.7.1. of the accompanying master protocol:

Vaccines to be evaluated in sub-protocols under the master protocol will be vaccines with marketing authorization at the time of each sub-protocol design and/or vaccines still in clinical development, i.e., pre-authorisation. Vaccines to be administered in the intervention and control arms will be defined in each sub-protocol depending on the hypothesis and the booster strategies tested.

Subjects allocated to control arms could receive a 3rd vaccine dose or not receive a 3rd vaccine dose.

Specific to this trial, Part B:

Study vaccines will be given as a 4th dose in subjects already vaccinated with defined prior vaccination strategies (with BNT162b2, mRNA-1271 or ChAdOx-1-S) as per eligibility criteria. The

vaccines to be evaluated as 4th vaccination (second booster) dose will be BNT162b2 (Comirnaty®) and mRNA-1273 (Spikevax®). For a detailed overview of all cohorts and arms in this study please refer to Tables 2.1 and 2.2 below.

In Part B there is a minimum interval of 1 month between the on-study 4th vaccination dose and the 3rd pre-study vaccination, with longer intervals as per local regulation or practice.

Table 2.1: **Intervention in Part A** no longer active - for information only

Cohort	Vaccination prior to study entry	Arm	Study intervention: 3 rd vaccination dose	Part A with Cohorts 1 to 3 closed to further recruitment as of January 13, 2022
Cohort 1	BNT162b2 + BNT162b2	1	BNT162b2	
		2	mRNA-1273	
Cohort 2	mRNA-1273 + mRNA-1273	3	BNT162b2	
		4	mRNA-1273	
Cohort 3	ChAdOx-1-S + ChAdOx-1-S	5	BNT162b2	
		6	mRNA-1273	
Control	Control arm of the EU-COVAT subprotocol EudraCT no. 2021-004889-35, a separate sub-protocol embedded within the EU-COVAT master protocol, will be used for a descriptive comparison.			

Table 2.2: **Intervention in Part B - 4th vaccination dose**

Cohort	Vaccination prior to study entry	Arm	Study intervention: 4 th vaccination dose*
Cohort 4	BNT162b2 + BNT162b2 + BNT162b2	7	BNT162b2
		8	mRNA-1273
Cohort 5	BNT162b2 + BNT162b2 + mRNA-1273	9	BNT162b2
		10	mRNA-1273
Cohort 6	mRNA-1273 + mRNA-1273 + mRNA-1273	11	BNT162b2
		12	mRNA-1273
Cohort 7	mRNA-1273 + mRNA-1273 + BNT162b2	13	BNT162b2
		14	mRNA-1273
Cohort 8	ChAdOx-1-S + ChAdOx-1-S + BNT162b2	15	BNT162b2
		16	mRNA-1273
Cohort 9	ChAdOx-1-S + ChAdOx-1-S + mRNA-1273	17	BNT162b2
		18	mRNA-1273

* administered at least 1 month after the 3rd pre-study vaccination.

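### The time-lag sensitivity analysis of the responder endpoint (SAP 9.3.1) names only the 2nd-to-3rd dose interval; SAP 9.4.3 also names the 3rd-to-4th interval, which bears more directly on this endpoint

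*SAP*

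**What the plan says.** SAP 9.3 defines response as a 2-fold rise in anti-RBD titre measured "at 14 days after the 4th vaccine dose (versus immediately before vaccination"). The primary analysis is the observed rate per randomised group with Clopper-Pearson intervals; no model is involved.

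SAP 9.3.1 adds supportive logistic models for the same endpoint, in which "we will also adjust for factors such as initial vaccination regimens (factor cohort), age and sex". A sensitivity analysis follows: "We will also account for the different time lags between the 2nd and 3rd doses in further sensitivity analysis", for example by "including the number of days between vaccinations as additional covariate in the analysis models". No other interval is named.

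SAP 9.4.3 presents the adjustment of the repeated-measures models as following those logistic models, but there the time lags are "for the time between the 2nd and 3rd doses and between the 3rd and 4th doses, respectively in further sensitivity analysis".

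On the interval itself, Protocol 4.7.1 says that "there is a minimum interval of 1 month between the on-study 4th vaccination dose and the 3rd pre-study vaccination" and allows longer gaps according to local rules or practice. No maximum is given. Protocol 4.7.5 and SAP 6 stratify randomisation by prior vaccine series, gender and documented prior COVID-19. Neither the interval nor the trial site is a stratification factor.

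SAP 9.5 plans exploratory comparisons of the primary endpoint between cohorts.

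**The concern.** The denominator of the fold rise is the titre remaining after the 3rd dose. If that titre wanes, someone vaccinated soon after the 3rd dose starts higher and has more difficulty doubling than someone vaccinated much later. The 3rd-to-4th interval is therefore a likely prognostic factor for response, and the 2nd-to-3rd interval lies one dose further back. The SAP treats the more recent interval as relevant for the secondary models but does not name it for the responder models.

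Two supportive or exploratory results are exposed. The arm odds ratio is estimated without a likely prognostic covariate. The between-cohort comparisons are not randomised, so cohorts that differ in time since the 3rd dose could appear to differ because of their prior vaccine series.

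**Working it through.** **1. The plan's own figures.** These come from Protocol 6.3 and SAP 12.1: 250 per group, proportion 0.5, two-sided 0.05 with Bonferroni for two intervals.

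- Half-width = z(1 − 0.025/2) × √(0.25/n) = 2.2414 × √(0.25/250) = 0.0709, against 0.071 stated.
- At n = 90 the result is 0.118 and at n = 40 it is 0.177, both as tabulated.
- Total N = 500/(1 − d) = 544, 550 and 556 for dropout d of 8%, 9% and 10%, against 550 stated.

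No interval between doses enters any of these formulas, so the choice of lag covariate cannot change them.

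**2. The sections side by side.**

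| Place | Outcome | Lags named |
|---|---|---|
| SAP 9.3 | responder rate, unadjusted | none |
| SAP 9.3.1, main logistic model | responder | none (cohort, age, sex; open list) |
| SAP 9.3.1, sensitivity analysis | responder | 2nd-to-3rd |
| SAP 9.4.3, sensitivity analysis | titre, repeated measures | 2nd-to-3rd and 3rd-to-4th |
| SAP 16.3 (Part A) | responder | lags between vaccinations, no pair specified |

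The gap is in the third row.

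**3. Illustration of the arm comparison.** The documents give neither the distribution of the interval nor its effect on response, so the following is assumed. The interval t is standard normal, and logit P(response) = β·g + ln(k)·t, where g is the arm and k is the odds ratio for response per SD of interval, set to 1.0, 1.5, 2.0 and 3.0. Allocation is 1:1.

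- *No true arm effect* (β = 0, 250 per arm, 4,000 simulated trials, t omitted): mean difference in rates at most 0.001 in absolute value. Type I error was 0.052 to 0.062, with no trend in k; it was 0.057 at k = 1.0, where the interval has no effect at all.
- *Conditional arm odds ratio of 2.0* (β = ln 2): with t omitted, the odds ratio appears as 2.00, 1.96, 1.87 and 1.74 for the four values of k. This is non-collapsibility, towards 1, and not confounding.

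**4. Illustration of the between-cohort comparison.** Same model with no arm or cohort effect; two cohorts have mean intervals 1 SD apart, t ~ N(+0.5, 1) and N(−0.5, 1).

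| k per SD of interval | Responder rates in the two cohorts |
|---|---|
| 1.0 | 50% / 50% |
| 1.5 | 55% / 45% |
| 2.0 | 58% / 42% |
| 3.0 | 61% / 39% |

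The differences come from the interval alone. Whether the cohorts in this trial differ by 1 SD, by less or not at all is not in the documents.

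**The case against.** The strongest reply is that the SAP leaves room for the interval and covers it elsewhere. The covariate list in 9.3.1 is open, the days-between-vaccinations clause is given as an example, and 9.4.3 describes its own adjustment as similar. In addition, "the antibody titre values of visit 1 and 2 will be analysed on the metric scale" with a reference to the secondary analyses, where both lags are named and the repeated-measures model includes baseline titre. This makes a drafting slip more likely than a deliberate exclusion. It does not close the gap: the example concerns how a lag enters the model, while the sentence itself says which lag is meant. The metric-scale analysis has a different outcome and does not adjust the responder odds ratio or the between-cohort responder comparisons.

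A second reply is that the comparisons most exposed are exploratory, and SAP 9.8 rules out extrapolating between cohorts in the primary analysis. That stands and limits the severity.

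A reader might also infer three stronger things that the documents do not support:

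- *That waning biases the primary result or the arm comparison.* The primary analysis has no model, and 1:1 randomisation stratified by prior series balances the interval in expectation, overall and within each cohort.
- *That adding the covariate would correct the cohort-specific rates.* Those are unadjusted proportions and would be reported unchanged.
- *That the distortion is large relative to the planned precision.* Differences of 16 to 19 percentage points between cohorts can be generated from assumed titre half-lives of 60 to 120 days and mean intervals 60 days apart, but those inputs, and the assumed size and spread of the fold rise, come from outside the documents. Setting such a difference against ±7.1 points is also the wrong comparison: that is the half-width for one pooled group of 250. The SAP's table gives 11.8 to 17.7 points for a single rate at n = 90 to 40, and a difference between two such rates is less precise still.

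**Conclusion.** The inconsistency is real and minor. SAP 9.3.1 limits the time-lag sensitivity analysis of the responder endpoint to the less directly relevant interval, while 9.4.3 names both. The primary rates, their intervals, alpha, the sample size and the validity of the randomised comparison are unaffected. What remains is some attenuation of the supportive arm odds ratio (2.0 appearing as 1.74 to 1.96 if the interval effect is an odds ratio of 1.5 to 3.0 per SD) and possible confounding of the exploratory between-cohort responder comparisons. The first figure depends on the assumed interval effects; the size of the second cannot be derived from the documents.

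**What to change.** - In SAP 9.3.1, name both the 2nd-to-3rd and the 3rd-to-4th dose intervals in the time-lag sensitivity analysis, matching 9.4.3.
- In SAP 9.5, include days since the 3rd dose as a covariate in the between-cohort comparisons of the primary endpoint.
- Describe the distribution of that interval by arm and cohort.
- Optionally, tabulate responder rates by band of days since the 3rd dose, descriptively and where numbers allow; small cohorts may be too sparse.

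The cost is a few words in 9.3.1, a sentence in 9.5 and one descriptive table. The vaccination dates are already needed for 9.4.3, so no new data are collected, and no sample-size or alpha figure changes.
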